18.1.4 Determining Attribution to the Investigational Agent(s)

Attribution: An assessment of the relationship between the AE and the medical intervention. CTCAE does not define an AE as necessarily “*caused by a therapeutic intervention*”. AEs will be monitored until they are resolved or are clearly determined to be due to a subject’s stable or chronic condition or intercurrent illness.

After naming and grading the event, the clinical investigator must assign an attribution; or the determination of whether an adverse event is related to a medical treatment or procedure. The categories of attribution are described below:

Relationship	Attribution	Description
Unrelated to investigational agent/intervention	Unrelated	The AE is clearly NOT related
	Unlikely	The AE is doubtfully related
Related to investigational agent/intervention	Possible	The AE may be related
	Probable	The AE is likely related
	Definite	The AE is clearly related

18.1.5 Serious Adverse Event (SAE)

A serious adverse event is any untoward medical occurrence resulting in one or more of the following:

- Results in death or ANY death occurring within 28 days of last dose of study drug (even if it is not felt to be drug related)
- Is life-threatening (defined as an event in which the patient was at risk of death at the time of the event; it does not refer to an event which hypothetically might have caused death if it were more severe)
- Requires inpatient hospitalization or prolongation of existing hospitalization
NOTE: Hospitalizations that are not considered SAEs are:
 - Hospitalization planned prior to first administration of study drug
 - Hospitalization for elective treatment of a pre-existing condition unrelated to the study medication
- Results in persistent or significant disability/incapacity
- Is a congenital anomaly or birth defect
- Is an important medical event (defined as a medical event(s) that may not be immediately life-threatening or result in death or hospitalization but, based upon appropriate medical and scientific judgment, may jeopardize the patient or may require intervention (e.g. medical, surgical) to prevent one of the other serious outcomes listed in the definition above). Examples of such events include, but are not limited to, intensive treatment in an emergency room or at home for allergic bronchospasm; blood dyscrasias or convulsions not resulting in hospitalization; or the development of drug dependency or drug abuse.
- Pregnancy
Pregnancy of a patient or of the female partner of a male patient during the study or within 30 days after the last dose of study drug should be reported via an SAE report. Should pregnancy occur in a female participant during the treatment

period, study drug should be discontinued immediately. Should a pregnancy occur in a female companion of a male participant during the treatment period, the male participant can continue treatment immediately. Any such pregnancy is to be followed until final outcome.

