9.2 Surgical Resection

Approximately 4 weeks (+/- 2 weeks) after the completion of the neoadjuvant treatment, patients will undergo standard of care operative exploration and complete extirpative surgery. Operative planning will be based on the original review of the patients' initial (i.e. pre-treatment) staging CT or MRI scan and the scan obtained after completion of the neoadjuvant protocol. All patients will undergo two modalities of operative exploration for occult metastatic disease undetectable with conventional cross-sectional imaging. Prior to laparotomy, patients will undergo a formal two-port staging laparoscopy to exclude the presence of occult metastatic disease involving the liver or peritoneal surfaces. Suspicious nodules possibly representing metastatic disease will be biopsied to confirm a pathologic diagnosis of metastatic pancreatic adenocarcinoma. Proof of metastatic cancer (i.e. stage IV cancer) will exclude patients from operative resection of the primary pancreatic cancer. In the absence of metastatic disease detectable with staging laparoscopy, patients will undergo a formal laparotomy with abdominal exploration to exclude occult metastatic disease involving the peritoneal surfaces or liver.

In the absence of occult metastatic disease, patients will undergo the planned operative procedure to resect the primary pancreatic adenocarcinoma completely. Based on preoperative imaging,

patients will undergo either a pancreatoduodenectomy (PD) or distal pancreatectomy and splenectomy (DPS). PD will be performed for patients with head and/or neck of pancreas cancers. DPS will be performed for patients with body and/or tail of pancreas cancers. PD and DPS will be performed according to standardized techniques which are employed routinely at Indiana University Hospital.

All margins of resection will be sampled intraoperatively to ensure complete clearance. For PD, the neck of pancreas and bile margins will be reviewed with frozen section histopathologic analysis. For DPS, the proximal pancreatic margin (i.e. body or neck of pancreas) will be reviewed intraoperatively. Final margin status (R0 versus R1) of the resected specimens will be recorded in addition to the intraoperative margin status assessments.

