All complications within 30 days of operative resection will be recorded prospectively and comprehensively according to the data acquisition guidelines of the American College of Surgeons National Surgical Quality Improvement Program (ACS-NSQIP). All patients undergoing pancreatectomy at Indiana University Hospital are included in the ACS-NSQIP database which has been modified to contain complications variables specific to pancreatic procedures.

Patients will receive a routine, formal clinical evaluation by their respective surgeon as per institutional guidelines and standard of care. Postoperative complications will be recorded during this evaluation and will be treated according to standardized practices. Patients will be evaluated for post-operative adjuvant chemotherapy within 4-6 weeks from the date of the operation as is routinely done after surgery. Further adjuvant treatment will be determined at the treating physician's discretion (i.e. chemoradiotherapy or adjuvant chemotherapy).

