18.2 Adverse Event (AE) Reporting

Adverse events (AEs) will be recorded from the time of first study drug administration and for at least 30 days after treatment discontinuation, regardless of whether or not the event(s) are considered related to trial medications. All AEs considered related to trial medication will be followed until resolution, return to baseline, or deemed clinically insignificant, even if this occurs post-trial.

18.2.1 Reporting to the Data Safety Monitoring Committee (DSMC):

Regardless of study sponsorship, the DSMC chair and/or coordinator will review all expedited SAE reports through OnCore®. Expedited reports are completed per IRB guidelines and may include the IRB Prompt Reporting form, and/or non-compliance form. Submission of this information to the DSMC is **additional to** any other protocol-specified regulatory bodies (e.g. FDA, pharmaceutical company) to be notified. When follow-up information is received, a follow-up report should also be created in OnCore®. The DSMC chair and/or coordinator will review expedited SAE reports monthly.

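### AE recording and the any-cause death limb of the SAE definition are timed from chemotherapy, so AE/SAE collection is not clearly required for most of the 30 days after surgery

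*Combined protocol and SAP*

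**What the plan says.** - **SAE definition (18.1.5).** The stem is broad: "A serious adverse event is any untoward medical occurrence resulting in one or more of the following". The death bullet has two limbs: "Results in death or ANY death occurring within 28 days" of the last dose. The first limb has no time limit and no attribution condition. The second, "ANY death occurring within 28 days of last dose of study drug (even if it is not felt to be drug related"), takes in deaths of any cause but closes at day 28.
- **AE recording (18.2).** AEs are recorded from first dosing and "for at least 30 days after treatment discontinuation, regardless of whether or not the event(s) are considered related to trial medications". This is a floor. Follow-up beyond it is promised only for AEs considered related to trial medication.
- **AE recording (Section 8).** Here 30 days after completion of neoadjuvant therapy, or progression, reads as an end point.
- **Study calendar (Section 10).** AE assessment last appears at the surgical evaluation/end-of-treatment visit. The long-term follow-up column has survival, progression and imaging only.
- **Surgery (9.2).** It takes place "Approximately 4 weeks (+/- 2 weeks) after the completion of the neoadjuvant treatment". In addition, "All complications within 30 days of operative resection will be recorded prospectively", under the surgical quality programme (ACS-NSQIP).
- **Oversight (15, 17.2, 18.2).** Deaths go on the CRF and to the IRB under local rules. SAE reports are entered in OnCore and reviewed monthly by the DSMC chair or coordinator. OnCore data are also monitored periodically by the DSMC.

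**The concern.** Preoperative chemotherapy can do harm through a worse operative outcome, and that harm appears after the operation. The protocol's AE and SAE clocks all start from chemotherapy: last dose, completion or discontinuation. None starts from surgery. With surgery planned around the time those clocks run out, a death three weeks after the operation and attributed to surgery can fall outside both the any-cause limb and the period in which AE recording is clearly required.

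What is at stake is safety oversight during enrolment. A run of postoperative deaths, each judged surgical, is not clearly required to enter the monthly SAE review. The stopping rule in 14.3 and 14.4 does not obviously compensate: it counts patients who cannot proceed to or complete surgery, and a patient who is operated on and then dies is not clearly among them.

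**Working it through.** The plan gives no figure of its own here, so there is nothing to reproduce. The check is calendar arithmetic.

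**Inputs**
- Any-cause death limb: closes on day 28 after the last dose (18.1.5).
- AE recording: required to day 30 (Section 8; a minimum in 18.2).
- Surgery: 4 weeks ± 2 weeks, so day 28 nominally, with a range of 28 − 14 = 14 to 28 + 14 = 42 (9.2).
- Postoperative period: 30 days (9.2), ending between day 14 + 30 = 44 and day 42 + 30 = 72.
- Time origin: first take completion to mean the last dose.

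**Formula.** For surgery on day s, a window closing on day w covers max(0, w − s)/30 of the postoperative period.

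| Surgery day s | 28-day death limb | 30-day AE window |
|---|---|---|
| 14 | 14/30 = 47% | 16/30 = 53% |
| 21 | 7/30 = 23% | 9/30 = 30% |
| 28 | 0% | 2/30 = 7% |
| 35 | 0% | 0% |
| 42 | 0% | 0% |

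**Average, assuming surgery is uniform over days 14 to 42 (a span of 28 days).** Integrating (w − s)/30 from 14 to w and dividing by 28 gives (w − 14)²/(2 × 30 × 28):
- 28-day limb: 14²/1680 = 196/1680 = 11.7%.
- 30-day window: 16²/1680 = 256/1680 = 15.2%.

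Counting whole days inclusively (31 postoperative days, 29 possible surgery days) gives 120/899 = 13% and 153/899 = 17%, so the conclusion does not depend on the counting convention.

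**Other reading of the origin.** The last planned dose is on day 15 of cycle 2. If completion means the end of that 28-day cycle, surgery moves 28 − 15 = 13 days later relative to the last dose: nominally day 41, range 27 to 55. The 28-day limb then covers at most (28 − 27)/30 = 3%. The AE window keeps the coverage shown in the table if its 30 days run from the same completion date, and covers at most (30 − 27)/30 = 10% if they run from the last dose.

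**What the arithmetic shows.** Moving the death limb from 28 to 30 days would raise average coverage only from 11.7% to 15.2%. Only a window counted from the operation closes the gap.

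**Where the other records lead**
- CRF and surgical database: no section states that deaths recorded there enter the monthly SAE review.
- IRB: prompt reporting under 18.2.2 requires harm, unexpectedness and at least possible relatedness to the research. A death judged purely surgical fails the last condition and, even as an SAE, can wait for continuing review.

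**The case against.** A reader might infer that most operative deaths need not be reported as SAEs. The text does not support that. The first death limb has no clock and no relatedness test, so a fatal leak or haemorrhage on day 29, 45 or 60 satisfies the SAE definition. The 28-day limb only adds deaths; it excludes none.

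Nor does the mismatch between 28 and 30 days do much by itself. A fatal AE on day 29 or 30 falls within required AE recording and is an SAE under the first limb.

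It would also be wrong to say that such deaths go unseen. They are on the CRF, in the 30-day surgical record and subject to local IRB rules. OnCore data are periodically monitored by the DSMC, investigators review safety continuously with monthly summaries to the DSMC, and the DSMC can itself suspend or close the study.

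All of that stands. What remains is that a definition is not a duty to collect. Section 8 reads as an end point, the 18.2 minimum permits longer recording without requiring it, and the calendar schedules no AE assessment after the end-of-treatment visit. The alternative records are not stated to feed the SAE review.

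One might add that relabelling such deaths as SAEs gains little, because 18.2.1 describes DSMC review of expedited reports and a death judged unrelated would not be expedited. But 17.2 describes monthly entry and review of SAE reports without that restriction, and the gain from the fix rests on that provision.

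**Conclusion.** The point holds as a gap in required collection, not as a gap in the SAE definition. Both the any-cause death limb and AE recording end about 28 to 30 days after chemotherapy, while the 30-day postoperative period ends 44 to 72 days after it. If completion means the last dose and surgery is uniform over days 14 to 42, the any-cause limb covers about 12% of postoperative days and the AE window about 15%. The limb covers nothing for surgery on day 28 or later.

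The uniform timing is an assumption. The percentages are shares of calendar days and ignore the untimed death limb. The documents give no operative mortality or timing of deaths, so no share of deaths can be derived. The statement that the limb closes on the nominal day of surgery also depends on completion meaning the last dose.

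This is a worthwhile, inexpensive improvement to safety reporting. It does not touch the primary pCR analysis or its power.

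**What to change.** - **18.1.5:** make any death within 30 days of the last dose of study drug or within 30 days of the operation, whichever is later, an SAE regardless of attribution. Define the operation to include laparoscopy or laparotomy that ends without resection, since 9.2 provides for that outcome and a clause tied to resection would miss those patients.
- **Section 8 and 18.2:** align the recording windows with this, using the 30-day postoperative period already in 9.2. State one time origin in place of the present mix of last dose, completion and discontinuation, and say whether 30 days is a minimum or an end point.

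The cost is one sentence in 18.1.5, matching edits in the two recording sections, and a few additional SAE reports for deaths that are already captured on the CRF.

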18.2 Adverse Event (AE) Reporting

Adverse events (AEs) will be recorded from the time of first study drug administration and for at least 30 days after treatment discontinuation, regardless of whether or not the event(s) are considered related to trial medications. All AEs considered related to trial medication will be followed until resolution, return to baseline, or deemed clinically insignificant, even if this occurs post-trial.

18.2.1 Reporting to the Data Safety Monitoring Committee (DSMC):

Regardless of study sponsorship, the DSMC chair and/or coordinator will review all expedited SAE reports through OnCore®. Expedited reports are completed per IRB guidelines and may include the IRB Prompt Reporting form, and/or non-compliance form. Submission of this information to the DSMC is **additional to** any other protocol-specified regulatory bodies (e.g. FDA, pharmaceutical company) to be notified. When follow-up information is received, a follow-up report should also be created in OnCore®. The DSMC chair and/or coordinator will review expedited SAE reports monthly.

18.2.2 Reporting to the IRB

Each participating site will report adverse events and unanticipated problems to their IRB per local guidelines. Any event that requires expedited reporting to the local IRB will also be submitted to the IU Simon Cancer Center.

Unanticipated problems involving risks to subjects or others will be reported **promptly** to the IRB if they:

- caused harm;
- were unexpected; AND
- were related or possibly related to the research intervention.

If the serious adverse event does not meet all three (3) criteria listed above, the event does not have to be promptly reported to the Indiana University IRB. However, it should be reported at the time of continuing review.

Prompt reporting of unanticipated problems to the IRB is defined as within 5 business days from becoming aware of the event.

18.3 Record Retention

All documentation of adverse events and records of all IRB correspondence will be stored in accordance with all applicable federal guidelines.

21. APPENDICES

Appendix I

NCI Common Toxicity Criteria

Version 4.0

Due to the size of the latest version of the Common Toxicity Criteria, copies of this appendix are not included with this protocol document.

An electronic copy is available on the CTEP web site, <http://ctep.cancer.gov/reporting/ctc.html>

Appendix II
Performance Status Scales/Scores

ECOG or Zubrod		Karnofsky		Lansky	
Score	Activity	Score	Activity	Score	Activity
0	Fully active, able to carry on all pre-disease performance without restriction.	100	Normal, no complaints, no evidence of disease.	100	Fully active, normal.
		90	Able to carry on normal activity; minor signs or symptoms of disease.	90	Minor restrictions in physically strenuous activity.
1	Restricted in physically strenuous activity but ambulatory and able to carry out work of a light or sedentary nature, e.g. light housework, office work.	80	Normal activity with effort; some signs or symptoms of disease.	80	Active, but tires more quickly.
		70	Cares for self, unable to carry on normal activity or do active work.	70	Both greater restriction of and less time spent in play activity.
2	Ambulatory and capable of all selfcare but unable to carry out any work activities. Up and about more than 50% of waking hours.	60	Requires occasional assistance, but is able to care for most of his/her needs.	60	Up and around, but minimal active play; keeps busy with quieter activities.
		50	Requires considerable assistance and frequent medical care.	50	Gets dressed, but lies around much of the day; no active play; able to participate in all quiet play and activities.
3	Capable of only limited selfcare, confined to bed or chair more than 50% of waking hours.	40	Disabled, requires special care and assistance.	40	Mostly in bed; participates in quiet activities.
		30	Severely disabled, hospitalization indicated. Death not imminent.	30	In bed; needs assistance even for quiet play.
4	Completely disabled. Cannot carry on any selfcare. Totally confined to bed or chair.	20	Very sick, hospitalization indicated. Death not imminent.	20	Often sleeping; play entirely limited to very passive activities.
		10	Moribund, fatal processes progressing rapidly.	10	No play; does not get out of bed.

Appendix III DSMC Check Sheet

Meeting Minutes Form for DSMC
send to [contact] or file in binder

Meeting Date:			
Team/Program: (include meeting sign in sheet)			
Protocol & Status (open/closed to accrual) (one protocol per sheet)			
PI:			
	Y	N	
Weekly and Monthly meetings should include discussion on data, dose levels, accrual numbers, deviation summaries and SAE reports (per IUSCC DSMP).			
Has accrual been reviewed and entered into Oncore?			
Have all SAE's been entered into Oncore?			
Is there documentation for study discontinuation?			
Have all deviations been entered into OnCore?			
Have study deviation summaries been reviewed by the team (CTO continue to keep deviation logs signed by PI) ?			
Record any dose limiting toxicities (DLT's) on this form for any phase I investigator initiated trial, HOG or on a multi-site trial in which IUSCC is the lead site.			
If any of your answers are "NO" please explain in the space below.			
*Notes			

This form is to be used for Investigator Initiated and HOG trials (High risk weekly, Moderate risk Monthly, Low risk quarterly)

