14.4 Criteria for stopping study

The study will be discontinued if 25-30% of patients are unable to complete surgery due to toxicity. Analysis will be conducted after the first 20 patients are enrolled onto the study. If >6 patients are not able to proceed with surgery due to excessive toxicity the study will discontinue due to unacceptable toxicity.

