17.2 Data and Safety Monitoring Plan

This trial will comply with the current requirements of the Data and Safety Monitoring Plan (DSMP) of the IUSCC. The CTO of the IUSCC will be the Coordinating Center for this phase 2 trial. Investigators will conduct continuous review of data and patient safety. **Monthly review meetings** are required and will include the Principal Investigator, clinical research specialist and/or study nurse (or other members will be present at the Principal Investigator's discretion). **Monthly** meeting summaries should include review of data, the number of patients, significant toxicities as described in the protocol, and responses observed. Summaries will be submitted to [contact] and reviewed monthly by DSMC. **Monthly** meeting summaries will include and document review of data and patient safety by including: the number of patients, significant toxicities as described in the protocol, responses observed, eligibility of patients enrolled at each site, serious adverse events (SAEs) or unanticipated problems (UPs) (both IUSCC and those reported from other institutions), dose adjustments, and protocol deviations. Meeting minutes will be submitted and reviewed by the DSMC.

Study Monitoring for Moderate Risk Trials

All trials conducted at the IUSCC are subject to auditing and/or monitoring. Reports will be reviewed by the full DSMC at the time of study review (Reference Risk Table in full DSMC Charter).

Early Study Closure

At any time during the conduct of the trial, if it is the opinion of the investigators that the risks (or benefits) to the patient warrant early closure of the study, this recommendation should be made in writing to the Data Safety Monitoring Committee. Alternatively, the DSMC may initiate suspension or early closure of the study based on its review.

Reporting Guidelines

The DSMC has streamlined the reporting process by utilizing reports from OnCore[®]. This has allowed direct view of reports within the Clinical Trials Management System (CTMS); thus, discontinuing all paper reports. SAE reports are entered into OnCore[®] monthly and reviewed by the DSMC chair and/or coordinator monthly. Findings will be reported to the full DSMC at the time of the studies DSMC review.

Reporting Death

Death will be captured in the Case Report Form and reported per local IRB reporting guidelines.

Study Accrual Oversight

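### The stopping rule of more than 6 patients unable to reach surgery is applied once, at 20 enrolled, although a 7th failure settles it sooner, and the plan does not require that the DSMC be shown the count

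*Combined protocol and SAP*

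**What the plan says.** **The rule.** Section 14.3 (under Safety) and section 14.4 both stop the study if more than 6 patients cannot proceed to surgery. Section 14.4 fixes the timing: "Analysis will be conducted after the first 20 patients are enrolled onto the study". Section 14.3 counts failures from toxicity or progression and leaves out occult peritoneal metastases found only at surgery. Section 14.4 counts toxicity alone, and also expresses the criterion as 25-30% of patients. Neither section says who keeps the count, who receives it, or what happens if a 7th failure comes before the 20th enrolment.

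**Monthly reporting.** Section 17.2 says "meeting summaries should include review of data, the number of patients, significant toxicities as described in the protocol, and responses observed". It then adds eligibility, SAEs and unanticipated problems, dose adjustments and deviations. Routing is stated twice: "Summaries will be submitted to [contact] and reviewed monthly by DSMC" and "Meeting minutes will be submitted and reviewed by the DSMC".

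**The form.** Appendix III is the minutes form. Its header reads "send to [contact] or file in binder" and its prompt reads "Weekly and Monthly meetings should include discussion on data, dose levels, accrual numbers, deviation summaries and SAE reports". The items cover accrual, SAEs, deviations, dose-limiting toxicities for some trials, "Is there documentation for study discontinuation" and free notes. Its frequency line, "High risk weekly, Moderate risk Monthly, Low risk quarterly", makes it monthly here, since section 17.2 treats this as a moderate-risk trial.

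**The concern.** A patient who could not proceed to surgery stays counted. Once 7 of the first 20 have failed, no later outcome can bring the total back to 6 or fewer, so the stop is certain. A rule read only at 20 lets the trial go on enrolling and treating patients after its own criterion is met.

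Monthly reporting is the natural place for this to be noticed, but the count behind the plan's only numeric study-stopping rule is on neither the 17.2 list nor the form. The DSMC may close the study on its own review, and the plan does not ensure that the review includes this number. The form's header adds a contradiction: a team following it could file minutes that 17.2 requires to be submitted.

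**Working it through.** **1. The threshold in the plan's own terms.** More than 6 of 20 means at least 7, and 7/20 = 35%. But 25-30% of 20 is 5 to 6 patients. The count and the percentage in section 14.4 do not agree. The steps below use the count, 7.

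**2. Inputs.**
- Accrual: 2 patients per month (section 6).
- True failure rate p: not given, so assumed, from 25% to 60%. The range includes the 25-30% named in 14.4.
- Lag L from enrolment to a known failure: assumed, 1 to 3 months, the same for each patient.
- Check on the lag: the fourth dose falls on day 28 + 15 = 43, and surgery follows 4 (+/- 2) weeks after neoadjuvant treatment (section 9.2). Counted from day 43 this is day 57 to 85; counted from the end of cycle 2 (day 56) it is day 70 to 98. Surgical evaluation is therefore at roughly 2 to 3 months. A 1-month lag suits only early dropouts.

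**3. Formulas.** Let T be the enrolment number of the patient who is the 7th failure.
- P(T = k) = C(k-1, 6) p^7 (1-p)^(k-7)
- P(stop) = P(Bin(20, p) ≥ 7)
- The 7th failure is known when T + 2L patients have enrolled. It is known strictly before the 20th enrolment if T + 2L ≤ 19, with probability P(Bin(19-2L, p) ≥ 7). That is Bin(17, p) at 1 month and Bin(13, p) at 3 months.
- Mean enrolments spared given a stop = Σ max(0, 20 - 2L - k) P(T = k) / P(stop)

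**4. Results** (1-month lag to 3-month lag).

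| p | P(stop) | Known strictly before 20th enrolment | Mean enrolments spared, given a stop |
|---|---|---|---|
| 25% | 0.214 | 0.11 to 0.02 | 1.55 to 0.24 |
| 30% | 0.392 | 0.22 to 0.06 | 1.95 to 0.35 |
| 35% | 0.583 | 0.38 to 0.13 | 2.45 to 0.52 |
| 50% | 0.942 | 0.83 to 0.50 | 4.64 to 1.56 |
| 60% | 0.994 | 0.97 to 0.77 | 6.42 to 2.74 |

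Hand check: at p = 50% and 3 months, P(Bin(13, 0.5) ≥ 7) = 0.50 by symmetry.

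The third column is unconditional and the fourth is conditional on a stop. Multiplying the fourth by P(stop) gives the unconditional saving: at 35%, 2.45 × 0.583 = 1.43 and 0.52 × 0.583 = 0.30.

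**5. Error rates.** A running count reaches 7 within the first 20 patients exactly when the final count among those 20 is at least 7. With complete outcomes, P(stop) is therefore the same under either timing.

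**6. Reporting.** Set side by side, 17.2 requires submission and DSMC review of the minutes, while the Appendix III header offers filing as an alternative. Both list content, and neither lists patients unable to proceed to surgery.

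**The case against.** A reader might infer that the DSMC could receive nothing and that nobody need notice the threshold. The documents do not support that. Section 17.2 requires submission of summaries and of minutes. SAEs and deviations reach the DSMC chair or coordinator through OnCore whatever happens to the form. Investigators must review safety data continuously, and they or the DSMC can move to close the study at any time. The form has a discontinuation item and a notes field, and toxicities and responses need not be repeated there because 17.2 already requires them. The form also looks like an institutional template.

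A reader might also infer that a single look is an invalid design. It is not: one fixed look is a recognised choice, and letting it act early is an enhancement. At the failure rates the plan itself names, 25-30%, the saving at a realistic lag is well under one patient. Nor is there yet one agreed number to count, because 14.3 and 14.4 differ on cause.

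All of that stands and limits the size of the point. It does not remove it. None of those channels is required to carry the count, no text makes the threshold act before 20, and the header still contradicts 17.2. The disagreement over cause is a reason to report the count by reason, which serves either definition until the sponsor settles it.

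**Conclusion.** The point holds as a cheap improvement. The plan's own threshold can be met with certainty before the scheduled look, and the plan neither makes it take effect then nor requires that the DSMC see the count. At a 3-month lag the mean saving given a stop is 0.24 to 0.52 enrolments for true failure rates of 25-35%, and 1.56 to 2.74 for 50-60%. It is larger only if failures become known early.

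These figures rest on assumed failure rates, an assumed common lag, accrual of 2 per month, and a look taken as soon as the 20th patient enrols. The sample size, power and primary analysis are unaffected.

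**What to change.** 1. In section 14.4, state that the existing threshold takes effect as soon as it is reached among the first 20 patients, not only at the 20-patient look, and say who keeps the count.
2. In the section 17.2 monthly summary, add three cumulative figures: patients enrolled, patients with surgical outcome known, and patients unable to proceed to surgery, by reason. Add the same line to Appendix III.
3. Reconcile the Appendix III header with the submission requirement in 17.2.
4. Reconcile 14.3 with 14.4 on which causes count, and the 25-30% figure with more than 6 of 20. The choice is the sponsor's.

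The cost is a form edit, a few sentences and one extra count a month from data already collected. No patients are added, and the probability of stopping on complete data stays the same. The drawback is that the gain is small at moderate failure rates.
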